5.5 Supportive Care

5.5.1 All supportive measures consistent with optimal patient care will be given throughout the study.

5.5.2 Thrombosis Prophylaxis

5.5.2.1 Arm A

All patients on Arm A are to receive prophylaxis against thrombosis. For patients in Arm A, physicians should consider prophylaxis with aspirin alone as studies with single agent lenalidomide in the setting of relapsed disease show a relatively low incidence of thrombosis (<5%).

If the participant is on full-dose anticoagulation and it is anticipated that the course of therapy with full-dose anticoagulation is to be completed during participation in

this trial, the participant must then be placed on some form of anti-coagulation as prophylaxis.

Rev. 7/13

Arm	DVT prophylaxis	Acceptable alternative prophylaxis**
A	Aspirin each day of treatment cycle*	Lovenox 40 mg once a day subcutaneously or equivalent OR full dose coumadin targeting a therapeutic INR 2-3. For patients unable to tolerate 325 mg aspirin, 0 to 81 mg may be given.

Rev. 7/13

* Suggested dose of Aspirin is 325 mg/day, however the dose is at the discretion of the treating physician. Alternative dosing of 75mg/day or higher is acceptable provided the patient is at low risk of thrombosis.

** Aspirin should not be given if patients are treated with alternative prophylaxis.

5.5.2.2 Prior or concurrent use of erythropoietin is disallowed.

5.5.2.3 Each site must have two trained counselors available for counseling all patients receiving lenalidomide supplied by the Division of Cancer Treatment and Diagnosis. Trained counselors must complete training using the online program provided free by Celgene, the Celgene Pregnancy Prevention Counseling Program (CPPCP) Registration for CPPCP is done by completing the form found in [Appendix XII](#) and following the directions provided in the email notification. After the training is complete, the counselors must generate a training certificate and provide it to the CTSU for documentation. Sites may not order lenalidomide until documentation for two trained counselors is provided to the appropriate office. The CPPCP forms can be faxed to the CTSU at [name].

Rev. 8/11, 1/16

Rev. Add14

5.6 Duration of Therapy

- Patients who progress to symptomatic myeloma at any time are discontinued from participation.
- Patients on Arm A of therapy are strongly encouraged to undergo growth factor based stem cell collection following 4-6 cycles of therapy.
- Patients are not permitted to undergo cyclophosphamide or other chemotherapy administration while on study for any reason, and specifically not for stem cell mobilization.

5.6.1 Extraordinary Medical Circumstances

Patients will receive protocol therapy unless:

If at any time the constraints of this protocol are detrimental to the patient's health, protocol treatment should be discontinued.

5.6.2 Patient withdraws consent.

5.6.3 Patient experiences progression of disease.

5.6.4 Patient experiences unacceptable toxicity.

5.6.5 Non-Protocol therapies are administered.

5.7 Duration of Follow Up

For this protocol, all patients, including those who discontinue protocol therapy early, will be followed for response until progression and for survival for 10 years from the date of randomization. All patients must also be followed through completion of all protocol therapy, and until PD, even if they initiate non-protocol therapy.

6. Measurement of Effect

Definitions of Stringent Complete Response, Complete Response, Very Good Partial Response, Partial Response, and Stable Disease are based on International Uniform Response Criteria for Multiple Myeloma and the American Society of Hematology/Food and Drug Administration consensus panel recommendations for the assessment of disease progression.(64)

6.1 Response Considerations

6.1.1 Terms and Definitions

6.1.1.1 M-Protein

Synonyms include M-spike, monoclonal protein and myeloma protein, monoclonal paraprotein, M-component.

6.1.1.2 Response Terms

The following response terms will be used: stringent complete response (sCR), complete response (CR), very good partial response (VGPR), partial response (PR), stable disease (SD), and progression (PD).

See Sections [6.2.1-6.2.6](#) for definitions.

6.1.1.3 Measurable Disease

Defined by at least one of the following three measurements

- Serum M protein ≥ 1 g/dL (≥ 10 gm/L)(10 g/L)
- Urine M protein ≥ 200 mg/24 hours
- Serum free light chain (FLC) assay: Involved free light chain level ≥ 10 mg/dL (≥ 100 mg/L) provided serum FLC ratio is abnormal

6.1.1.4 Evaluable Disease

Patients who do not have a “measurable” serum or urine M-spike.

6.1.1.5 Oligosecretory Myeloma

Patient with Multiple Myeloma who has NEVER had “measurable” disease, but has had a detectable monoclonal protein in his/her serum and/or urine.

6.1.1.6 Non-Secretory Myeloma

Patient with Multiple Myeloma who has NEVER had a detectable monoclonal protein in his/her serum and/or urine.

6.1.1.7 Response Evaluation and Confirmation

Except for assessment of sCR, CR, or VGPR patients with measurable disease restricted to the SPEP will need to be

followed only by SPEP; correspondingly, patients with measurable disease restricted to the UPEP will need to be followed only by UPEP.

Patients with measurable disease in either SPEP or UPEP or both will be assessed for response only based on these two tests and not by the FLC assay. FLC response criteria are only applicable to patients without measurable disease in the serum or urine.

To be considered CR, both serum and urine immunofixation must be carried out and be negative regardless of the size of baseline M-protein in the serum or urine.

In order to be classified as a sCR, CR, PR, or VGPR, confirmation of serum and urine monoclonal protein results is required and must be made at anytime before the institution of any new therapy. Confirmation is mandatory for sCR, CR, PR and VGPR documentation.

Bone marrow biopsy is required for CR; however, a repeat bone marrow biopsy is not needed for confirmation.

Bone radiographs are not required to document response. If bone radiographs are obtained, their findings must be consistent with the bone response criteria.

6.1.1.8 Oligosecretory and Non-secretory Myeloma

Patients with oligosecretory myeloma who have measurable levels on the serum FLC assay, are assessed for response using the FLC assay instead of serum and urine M-protein levels. All other requirements as outlined in each response category must be met. Patients with oligosecretory myeloma who do not have measurable levels on the serum FLC assay and patients with non-secretory myeloma may be assessed for response using bone marrow plasma cell involvement provided baseline bone marrow plasma cell percentage was $\geq 30\%$.

6.1.1.9 Bone Progression

Caution must be exercised to avoid rating progression or relapse on the basis of variation of radiologic technique alone. Compression fracture does not exclude continued response and may not indicate progression.

When progression is based on skeletal disease alone, it should be discussed with the study chair before removing the patient from the study.

6.1.2 Monoclonal Protein Considerations

Serum M-protein level is quantitated using densitometry on serum protein electrophoresis (SPEP) except in cases where the SPEP is

felt to be unreliable such as in patients with IgA monoclonal proteins migrating in the beta region. IF SPEP is not available or felt to be unreliable for routine M-protein quantitation during therapy, then quantitative immunoglobulin levels on nephelometry or turbidometry can be accepted. However, this must be explicitly reported; and only nephelometry can be used for that patient to assess response and SPEP and nephelometric values cannot be used interchangeably.

Urine M-protein measurement is estimated using 24-hour urine protein electrophoresis (UPEP) only. Random or 24 hour urine tests measuring kappa and lambda light chain levels are not reliable and are not allowed.

6.2 Response Categories

NOTE: For this protocol, patients will only have measurable serum and/or urine M-protein.

6.2.1 Stringent Complete Response (sCR)

CR as defined below plus all of the following:

- Normal serum FLC ratio at two consecutive times and
- Absence of clonal cells in bone marrow by immunohistochemistry, immunofluorescence, flow cytometry, or any other clonality determination method.^a

^a Presence/absence of clonal cells is based upon the k/λ ratio. An abnormal k/λ ratio by immunohistochemistry and/or immunofluorescence requires a minimum of 100 plasma cells for analysis. An abnormal ratio reflecting presence of an abnormal clone is k/λ of $> 4:1$ or $< 1:2$.

6.2.2 Complete Response (CR)

Patients who have complete disappearance of an M-protein and no evidence of myeloma in the bone marrow are considered to have complete response. To be considered CR, patients must meet all of the following criteria:

- Negative immunofixation on the serum and urine at two consecutive times, and
- Disappearance of any soft tissue plasmacytomas *and*
- $< 5\%$ plasma cells in bone marrow

6.2.3 Very Good Partial Response (VGPR)

- Serum and urine M-component detectable by immunofixation but not on electrophoresis *or*
- 90% or greater reduction in serum M-component plus urine M-component < 100 mg per 24 hours (by SPEP and UPEP)
- If the serum and urine M protein are unmeasurable and the immunoglobulin free light chain parameter is being used to measure response, a $\geq 90\%$ decrease in the difference between

involved and uninvolved free light chain (FLC) levels is required in place of the M protein criteria.

6.2.4 Partial Response (PR)

- Patients who have measurable disease in the serum at baseline require $\geq 50\%$ reduction in the level of serum M-protein (by SPEP).
- Patients who have measurable disease in the urine at baseline require $\geq 90\%$ reduction in the level of urine M-protein or the urine M-protein must be $< 200\text{mg}/24\text{hr}$ (by 24 hr UPEP).
- If the serum and urine M-protein are unmeasurable and the immunoglobulin free light chain parameter is being used to measure response, a $\geq 50\%$ decrease in the difference between involved and uninvolved free light chain (FLC) levels is required in place of the M-protein criteria.
- If serum and urine M-protein are unmeasurable, and serum free light assay is also unmeasurable, $\geq 50\%$ reduction in plasma cells is required in place of M-protein, provided baseline bone marrow plasma cell percentage was $\geq 30\%$.
- In addition to above listed criteria, if present at baseline, a $\geq 50\%$ reduction in size of soft tissue plasmacytomas is also required.

6.2.5 Stable Disease (SD)

Failure to meet response criteria outlined above.

6.2.6 Progression (PD)

The investigation that qualified as progression should be repeated and verified on a subsequent occasion only if treating physician deems it clinically necessary. Patients will be considered to have progression if both of the following criteria are met.(64)

1. Any one or more of the following:
 - Increase in serum M-protein to $\geq 25\%$ above the lowest response level, which must also be an absolute increase of at least $0.5\text{g}/\text{dl}$ to qualify as “progression.”
 - Increase in urine M-protein to $\geq 25\%$ above the lowest response level for 24-hour excretion, which also must be an absolute increase of at least $200\text{mg}/24$ hours of urine M-protein to qualify as “progression.”
 - Increase in bone marrow plasma cell percentage to $\geq 25\%$ from lowest response value (the absolute % increase must be $\geq 10\%$).

AND

2. Any one or more of the following felt related to the underlying clonal plasma cell proliferative disorder:
 - Hypercalcemia ($> 11 \text{ mg}/\text{dL}$)
 - Decrease in hemoglobin of $\geq 2 \text{ gms}/\text{dL}$

- Serum creatinine level \geq 2mg/dL
- Development of myeloma bone lesions or soft tissue plasmacytoma.

If subsequent verification is done, progression should be recorded as the date when the abnormality was first detected, not the date when it was confirmed.

6.3 Quality of Life Measurement

6.3.1 QOL Instruments

For the primary quality of life endpoint we will use a combined scale comprised of the well established and validated functional well-being (FWB) and physical wellbeing (PWB) components of FACT-G version 4 (14 questions), which will address the physical and functional well-being of SMM patients.

In addition, a new MM specific subscale (MMS) (14 questions) will be evaluated as a secondary endpoint. The MM subscale was developed in a three-step process using both expert and patient input. First, a pool of potential items was generated from the literature to create an item rating survey. These items were reviewed by thirteen health care providers with expertise in the diagnosis and treatment of Multiple Myeloma recruited through ECOG-ACRIN Myeloma Committee as well as from Mayo Clinic in Scottsdale, AZ, Mayo Clinic in Rochester, MN, and Marshfield Clinic in Marshfield, WI. Items were rated according to how common and how important they are when occurring in patients with this condition. Finally, experts were asked to circle up to 20 of the most important items (including self-nominated items) affecting patients with Multiple Myeloma. Expert input was compiled and ten additional items nominated during the surveys were added to the item rating survey. This survey was then formatted to be a semi-structured, self-administered, web-based interview that was conducted with a sample of forty-one MM patients. Identification and enrollment of eligible patients was performed using the International Myeloma Foundation website. Further candidate items were then generated by these patients using this semistructured interview designed to elicit personal experiences about how Multiple Myeloma and its treatment may affect physical status, emotional well-being, functional well-being, family/social issues, sexuality/intimacy, work status, and future orientation. Patients were also asked to complete the same item rating survey administered to the experts (with the additional ten questions) as well as answer basic disease and treatment questions. Patients were also given the opportunity to provide comments on items as well as additional feedback. Second, a team of CORE staff with extensive experience in QOL research, assessment and scale construction followed a standard process of item review and reduction as well as scale construction creating a final list of 14 items. Third, this final list of items was then reviewed by the Multi-Lingual Translation Team to screen for potential translation issues and to correct item wording in problematic instances.

6.3.2 Timing of QOL Assessments

The QOL assessment utilizing the FACT PWB+FWB and the MMS instruments will first be administered at registration (+ 7days) prior to initiation of treatment or observation. During the treatment or observation period, QOL will be measured every 6 cycles (day end + 7 days) up to cycle 48 and at the end of treatment (+ 14 days). For patients who discontinue protocol therapy or go off observation early not due to disease progression, QOL will also be assessed at the next quarterly Long Term follow-up visit (+ 14 days). After this, these patients will not be followed further for QOL.

7. Study Parameters for Arm A and Arm B

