2.3 Quality of Life Assessment Objectives

- 2.3.1 To compare QOL change between treatment and observation arms based on the functional (FWB) and physical (PWB) well-being components of the FACT-General (G) patient-reported outcome (PRO) measure from registration (prior to initiation of treatment) up to cycle 24.
- 2.3.2 To examine the impact of differential treatment response (PFS), if observed, on QOL based on the FACT FWB+PWB up to cycle 48.
- 2.3.3 To obtain prospective data on Myeloma specific QOL attributes, utilizing and evaluating the Multiple Myeloma Subscale (MMS).

3. Selection of Patients

Each of the criteria in the checklist that follows must be met in order for a patient to be considered eligible for this study. Use the checklist to confirm a patient's eligibility. For each patient, this checklist must be photocopied, completed and maintained in the patient's chart.

In calculating days of tests and measurements, the day a test or measurement is done is considered Day 0. Therefore, if a test is done on a Monday, the Monday four weeks later would be considered Day 28.

ECOG-ACRIN Patient No. _____

Patient's Initials (L, F, M) _____

Physician Signature and Date _____

NOTE: All questions regarding eligibility should be directed to the study chair or study chair liaison.

NOTE: Institutions may use the eligibility checklist as source documentation if it has been reviewed, signed, and dated prior to registration/randomization by the treating physician.

Rev. 7/14

NOTE: This study involves pre-registration (see Section 4). Bone marrow and peripheral blood specimens are to be submitted for defined laboratory research studies and future undefined research studies as outlined in Section 10 per patient consent.

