Patient enrollment will be facilitated using the Oncology Patient Enrollment Network (OPEN). OPEN is a web-based registration system available on a 24/7 basis. To access OPEN, the site user must have an active CTEP-IAM account (check at <https://eapps-ctep.nci.nih.gov/iam/index.jsp>) and a 'Registrar' role on either the LPO or participating organization roster.

All site staff will use OPEN to enroll patients to this study. It is integrated with the CTSU Enterprise System for regulatory and roster data. OPEN can be accessed at <https://open.ctsu.org> or from the OPEN tab on the CTSU members' side of the website at <https://www.ctsu.org>.

Prior to accessing OPEN site staff should verify the following:

- All eligibility criteria have been met within the protocol stated timeframes.
- All patients have signed an appropriate consent form and HIPAA authorization form (if applicable).

NOTE: The OPEN system will provide the site with a printable confirmation of registration and treatment information. Please print this confirmation for your records.

Further instructional information is provided on the OPEN tab of the CTSU members' side of the CTSU website at <https://www.ctsu.org> or at <https://open.ctsu.org>. For any additional questions contact the CTSU Help Desk at [name] or [contact].

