7.1 Therapeutic Parameters (for both arms of the study)

1. Prestudy scans and x-rays used to assess all measurable or non-measurable sites of disease must be done within **4 weeks** (28 days) prior to randomization/registration.
2. Prestudy CBC (with differential and platelet count) should be done **4 weeks** (28 days) before randomization/registration.
3. All required prestudy chemistries, as outlined in Section 3, should be done **4 weeks** (28 days) before randomization/registration unless specifically required on Day 1 as per protocol.

Rev. 8/11

Procedure	Prior to registration (≤ 28 days) ¹	10-14 days prior to starting Treatment or Observation	< 24 hours prior to starting Treatment or Observation	Induction- At the end of each Treatment or Observation cycle	Day 1 of each cycle	Studies needed to confirm sCR or CR	Periodically during Treatment or Observation	At study discontinuation or progression (whichever comes first)	28 Days after discontinuation of treatment	Post treatment to 10 years from study entry ¹¹
History and exam ⁶	X			X				X		X
Bone Marrow Aspirate and Biopsy ⁹	X					X				
ECOG Performance Status	X			X				X		X
NYHA Classification	X									
Chemistry labs ³	X			X				X		X
CBC with differential ⁴	X			X				X		X
Serum light chain assay	X			X		X		X		X
Serum immunoglobulin G, A, M	X			X				X		X
QOL ⁷	X			X				X		X

	SPEP	X			X				X		X
	Serum M-protein immunofixation	X					X				
	24 hr UPEP	X			X ^{2,10}				X ^{2,10}		X ^{2,10}
	Urine M-protein immunofixation	X					X				
	Metastatic bone survey	X						X ¹²	X		X ¹²
	ECG (12-lead)	X									
	Serum Pregnancy test for FCBP ⁵	X	X ⁵	X ⁵	X ⁵				X ⁵	X ⁵	
Rev. 8/11	Patient Education and Counseling ¹⁴	X		X	X	X			X	X	
	Serum Beta-2 microglobulin	X							X		
	C-reactive protein	X									
	LDH	X									
Rev. 8/11	Dispense lenalidomide ¹⁵			X		X					
Rev. 7/14	TSH (ARM A ONLY) ¹⁶	X									X ¹³
	Ultrasound ⁸				X						
	Documentation of oral drug				X						
	MRI (spine and pelvis)	X									
Rev. 12/13	Biological Sample Submissions	See Section 7.2									

1. Registration test results can be used for cycle 1 if less than 7 days before starting cycle 1.

-

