7. QOL timepoints: At registration (+ 7 days) prior to initiation of treatment or observation; the last day (+ 7) of cycles 6, 12, 18, 24, 30, 36, 42, and 48; and at the end of treatment or observation (+14 days). For patients that discontinue protocol therapy or go off observation early not due to disease progression, QOL will also be assessed at the next quarterly Long Term follow-up visit (+ 14 days). After this, patients will not be followed further for QOL.
8. If leg swelling or pain is present in legs, an ultrasound of the legs will be done for deep vein thrombosis.
9. Bone marrow biopsy or aspirate performed to evaluate plasma cells %, presence of sheets of plasma cells and presence of plasma cell clonality. Absence of plasma cell clonality required for sCR.
10. Needed if urine M-spike at study entry was ≥ 200 mg/24 hr or if VGPR needs to be documented.
11. Patients will be followed for progression every 3 months if patient is < 2 years from study entry, every 6 months if patient is 2-5 years from study entry, every 12 months if patient is 6-10 years from study entry. No specific requirements if patient is more than 10 years from study entry. Patients will be followed for survival only once progression occurs and study treatment ends.
12. To be repeated every year or if clinically indicated for progression or symptoms.
13. To be assessed every 4 months.
14. All patients must be counseled about pregnancy precautions, risks of fetal exposure and other risks. The counseling must be done on Day 1 of each cycle (or at a minimum of every 28 days) and at drug discontinuation. The Lenalidomide Education and Counseling Guidance Document ([Appendix VII](#)) must be completed and signed by a trained counselor at the participating site prior to each dispensing of lenalidomide treatment. A copy of this document must be maintained in the patient records. A Lenalidomide Information Sheet ([Appendix VIII](#)) will be supplied to each patient receiving lenalidomide treatment. The patient must read this document prior to starting lenalidomide study treatment and each time they receive new supply of study drug.
- Rev. 8/11 15. Only enough lenalidomide for 28 days or one cycle of study treatment may be provided to the patient each cycle.
- Rev. 8/11 16. TSH should be tested for Arm A ONLY and then only when clinically indicated by the Principal Investigator.
-

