9.7 Quality of Life

9.7.1 Primary QOL Endpoints

Quality of life assessment is performed in an identical fashion in both arms A and B and will be administered to both arms on the same schedule and frequency. The QOL assessment utilizing the FACT-

FWB+PWB and MMS instruments will first be administered at registration (+ 7 days) prior to initiation of treatment or observation. During the treatment or observation period, QOL will be measured every 6 cycles (day end + 7 days) and at the end of treatment or observation (+ 14 days). For patients that discontinue protocol therapy or go off observation early not due to disease progression, QOL will also be assessed at the next quarterly Long Term follow-up visit (+ 14 days). After this, these patients will not be followed further for QOL. Patients will be asked to complete the QOL questionnaire just prior to meeting with health care providers at scheduled visits. This should reduce the impact of health care related information upon perceived QOL.

The FACT-FWB+PWB PRO instrument has 14 items and the score ranges from 0-56. The primary endpoint for the QOL study will be defined as the mean change of the FACT-FWB+PWB score from registration (prior to randomization) to cycle 24. The null hypothesis is that the FACT-FWB+PWB mean change score between the two groups is the same over this time period. Based on the length of this PRO instrument, a minimal absolute difference in means change scores of the two arms of 4-6 is considered clinically significant between two groups.(70) Nevertheless, for this analysis the difference in drug-related QOL must be much greater to overcome a significant PFS benefit. The FACT- FWB+PWB domains are reported to have a standard deviation (SD) of 11. (Personal Correspondence with [name] dtd 12.26.08)

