9.7.2 Secondary QOL Endpoints

We will also explore the impact of the differential treatment survival (PFS) on the quality of life at certain clinically meaningful time points. More specifically, we will first evaluate the difference in the FACT-FWB+PWB mean scores between patients that experience disease progression (PD) and patients who do not experience PD using mixed effects model, where the longitudinal scores were collected from the following eight intervals:

- Interval 1: (registration prior to randomization – end cycle 6)
- Interval 2: (beg cycle 7 - end cycle 12)
- Interval 3: (beg cycle 13 - end cycle 18)
- Interval 4: (beg cycle 19 - end cycle 24)
- Interval 5: (beg cycle 25 - end cycle 30)
- Interval 6: (beg cycle 31 - end cycle 36)
- Interval 7: (beg cycle 37 - end cycle 42)
- Interval 8: (beg cycle 43 - end cycle 48)

Patients are included in the analysis of an interval if they have not failed up to the beginning of the interval. During an interval, for those patients that experience PD or discontinue treatment due to other reasons, the QOL assessment at the time of progression/ discontinuation will be used and for those who survive the interval, the QOL assessment at the end of the interval is used. We will also perform sensitivity for patients that did experience PD during the interval with respect to change in QOL status since last QOL assessment. Given the expected high level of missingness in the QOL data, we will analyze that data according to the methods described in Schluchter and in Schluchter, Greene and Beck.(71, 72)

These methods take into account the possibility of informative missingness by jointly modeling the longitudinal response (here, QOL scores) and the time to dropout.

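### The plan contradicts itself on whether the baseline of the primary QOL change score precedes randomization, and its 7-day rule permits a baseline collected after the arm may be known

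*Combined protocol and SAP*

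**What the plan says.** Three places give sites a window that opens at registration and runs for 7 days. Section 6.3.2 says the instruments "will first be administered at registration (+ 7days) prior to initiation of treatment or observation". Footnote 7 to the Section 7.1 schedule gives the time point as "At registration (+ 7 days) prior to initiation of treatment or observation". The opening paragraph of 9.7.1 repeats it. The only other limit in these places is the start of treatment or observation. The QOL objective in 2.3.1 fits this reading, since it measures change "from registration (prior to initiation of treatment) up to cycle 24" and does not mention randomization.

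Three places say something else. Section 9.7.1 defines the primary QOL endpoint as the "mean change of the FACT-FWB+PWB score from registration (prior to randomization) to cycle 24". Section 9.7.2 starts Interval 1 at "registration prior to randomization". The schedule table in 7.1 marks the baseline QOL form in the column "Prior to registration (≤ 28 days"), the same table whose footnote 7 allows a later form.

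**The concern.** A change score is only as clean as its baseline. Lenalidomide is compared with observation and no placebo is described, so a patient who has been told the assignment knows whether active treatment will follow. If the first form is completed after that, a reaction to the assignment can enter the baseline, and it may differ between arms. The randomized comparison of change scores then no longer starts from a value that randomization has balanced. Adjusting for that baseline would mean conditioning on a post-randomization measurement.

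The plan itself treats information as a possible influence on QOL answers: 9.7.1 has patients complete the form just before they meet providers, to limit the effect of health-care information. Learning the arm is information of the same kind, and the baseline enters every change score.

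**Working it through.** **Step 1: the rules side by side.**

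| Place | Baseline rule | Form after assignment permitted? |
|---|---|---|
| 6.3.2 | Registration + 7 days, before start | Yes |
| 7.1, footnote 7 | Same | Yes |
| 9.7.1, opening paragraph | Same | Yes |
| 2.3.1 | Before treatment | Not excluded |
| 9.7.1, endpoint definition | Registration, before randomization | No |
| 9.7.2, Interval 1 | Registration, before randomization | No |
| 7.1, schedule column | Before registration | No |

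Section 9.7.1 conflicts with itself, and the 7.1 table conflicts with its own footnote. The text extraction loses some symbols, so the plus sign may have been plus-or-minus. Either version allows a later form.

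**Step 2: is there a gap between registration and randomization?** If randomization came at least 7 days after registration, both sets of rules could hold. The documents do not describe that. Section 7.1 treats the two as one time point: a prestudy blood count "should be done 4 weeks (28 days) before randomization/registration". Section 4 describes pre-registration and registration, with no later randomization step. On that reading, a form completed in the days after registration follows randomization and does not meet the 9.7.1 definition.

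**Step 3: can the arm be known in the window?** In Section 4 (Patient Enrollment), "The OPEN system will provide the site with a printable confirmation of registration and treatment information". The same section says treatment should start within seven working days of registration, so the window lies in the interval between assignment and start. Footnote 14 of 7.1 requires lenalidomide patients to read an information sheet before starting. The site therefore has the arm at registration, and the patient may have it before the form is completed. No section says when the patient is told.

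**Step 4: what determines the size.** Let d_A and d_B be the mean reactions in points among late forms, and f_A and f_B the shares of late forms. Relative to a pre-randomization baseline, the A-minus-B difference in mean change moves by −(f_A·d_A − f_B·d_B). Equal reactions with equal shares cancel. If only one arm reacts, the movement is f·d in absolute size: for example, 25% late and an assumed 4-point reaction give 0.25 × 4 = 1 point.

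Persistence also matters. If a fraction p of the reaction remains at cycle 24, the reaction's net contribution to that arm's mean change is (p − f)·d. With all forms late (f = 1), this is −d if the reaction has gone (p = 0) and 0 if it persists fully (p = 1). The documents give none of f, d or p.

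**Step 5: an illustration, not an estimate.** Section 9.7.1 gives SD 11.0 and the example uses correlation 0.6. SD of change = 11.0 × √(2 × (1 − 0.6)) = 9.84, which reproduces the plan's value. Assume no true effect, a shift in the mean baseline of one arm, and no reaction left at cycle 24. The two-sided 0.05 t-test has noncentrality shift / (9.84 × √(2/n)), with n per arm. The plan's n = 38 (70% compliance) is not clearly per arm or total, so both readings are shown.

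| Assumed shift in arm mean | False-positive rate, 38 per arm | 19 per arm |
|---|---|---|
| 0 | 5.0% | 5.0% |
| 1 point | 7.2% | 6.1% |
| 2 points | 14.1% | 9.4% |
| 4 points | 41.7% | 23.0% |

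The clinically significant difference in 9.7.1 is 4-6 points. The plan's detectable difference of 8.1 points is not used as a yardstick, because it does not reproduce at 80% power: (1.960 + 0.842) × 9.84 × √(2/38) = 6.3 with 38 per arm, and with √(4/38) it is 8.9 with 38 in total. That is a separate matter, and this point does not depend on it.

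**The case against.** The strongest reply is that the plan already intends the right thing. The endpoint definition, Interval 1 and the schedule column all put the baseline before randomization or registration, so this is loose wording in the site instructions and not a chosen design. That stands, and it is why the point is a contradiction to be resolved.

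A reader might go further and infer that the baseline is collected with the arm known, that the reaction passes one-for-one into the change score, and that nothing can be done afterwards. The documents do not support any of these:

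- The confirmation goes to the site. When the patient learns the arm is not stated, and forms completed before assignment are unaffected.
- One-for-one transfer into an arm's mean change needs every form in that arm to be late and the reaction to be gone by cycle 24 (Step 4).
- If form dates are recorded, late baselines can be identified and set aside, so the problem is not beyond repair.
- No source gives a size in points, and nothing shows that physical and functional well-being scores move within days of an assignment, before any drug is taken.

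It is also fair to say that the consequences are limited. QOL is not the trial's primary endpoint, and 9.7.1 concedes that only large QOL differences can be detected at the expected compliance. What remains is that a site can follow 6.3.2 to the letter and return a baseline that does not meet the endpoint definition.

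**Conclusion.** The contradiction is established from the text. That post-assignment baselines are permitted follows from the 7-day rule, the single randomization/registration time point and the observation control. Bias in the between-arm change score is possible but not shown. Its direction is unknown, and its size depends on the share of late forms in each arm and on how much of any reaction remains at cycle 24. The rates in Step 5 hold only under the shifts assumed there.

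The conclusion rests on two inferences: that registration and randomization coincide, as 7.1 writes them, and that some patients learn the arm before completing the form. Low severity; a cheap improvement.

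**What to change.** In 6.3.2, footnote 7 of 7.1 and the opening paragraph of 9.7.1, replace the 7-day window with a requirement that the baseline form be completed after consent and before randomization. The existing pre-registration step is one place to do this. Record the form's date relative to assignment, report the number of later forms by arm, and prespecify a sensitivity analysis that excludes baselines dated after randomization. Exclusion after randomization can itself select patients, so it should support the main analysis and not replace it.

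Section 9.2 expected enrolment to finish about 24 months after June 2015, and this version carries a risk list dated June 2019, so enrolment may have ended, although the documents do not say so. In that case only the dating and the sensitivity analysis apply.

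The cost is some wording, a site instruction and one extra analysis. The downside is that a few baseline forms the window would have captured may be missed or excluded.
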